The force will be defined relative to maximum voluntary contraction for each hand separately. This allows even low-functioning participants to perform the task with the paretic hand. The participants will receive the instruction to follow the imperative cue by adjusting their own grip force. Feedback will be provided about the actual grip force in real-time. Force adjustment happens in stepwise increments of the relative force, which allows to induce two different implicit learning modes. Specifically, the volunteers will learn the association between visual cue and individual force level (1st order) within standard serial reaction time task⁴⁹, in which a sequence of force levels is provided repetitively and contrasted with random force levels. In addition, they will learn the hidden rule, i.e., the 2nd order sequence that can occur among both, the first-order sequential and the random force levels. This hidden regularity will be implemented through the sequential variation of cue intervals comparable to a morse code that occurs among otherwise uniform intervals. Based on the recorded muscle force (1000Hz sampling rate), the behavioral outcome (temporal/spatial accuracy) is monitored continuously throughout the learning phase. This procedure makes it possible to differentiate performance in the two learning modes. Furthermore, as left and right hand will be tested, it will be possible to estimate the impact of hand-dominance and side of lesion (non-/paretic hand) on the learning capacity for each learning mode.

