Imaging Parameters (sessions 3 and 4). Scanning will take place at the Center for Biomedical Imaging on the Siemens 3T Prisma. Functional and structural scanning parameters are detailed in the **NI Core**. High-resolution structural, fluid-attenuated inversion recovery (FLAIR), diffusion-weighted (DWI), and arterial spin labeling (ASL) perfusion imaging will use in-house standard sequences and will be collected from all participants in session 3. The task-based fMRI sequence will be optimized for an event-related design with a TR of 2 seconds. For the resting-state data, a TR of 0.8 seconds will be used. Task-based and resting-state imaging will be collected in session 4 with varying protocols for participants of SG and CG as described in the timeline below and explicitly detailed in the information and consent form. All MRI sequences will be accompanied by electrical recording of physiological signals from the upper body (e.g., electrocardiogram, electrodermal analyses) to support processing of MRI data and for secondary analyses examining relationships between autonomic nervous system dysfunction, brain, and behavioral outcomes.

D2. TIMELINE

Participants of both groups (stroke, control) will undergo the same protocol, which includes 4 sessions (outlined in the table below).

Session Number	Task Description	Location at Medical University of South Carolina	Approximate Time Commitment
0	Telephone Eligibility Screening 
 • Sensorimotor function screening (Appendix 1) • Cognitive screening (TICS^{26,27}) • MRI Safety Screen 	Via telephone	30 minutes
1	Consent	Stroke Recovery Research Center or remotely through electronic consent	20-30 minutes
2	Multi-system Assessment 
All participants
 
 • Pregnancy Test • EHI[§] • Questionnaires (Appendix 2)[§] • Neuro-Cognitive and emotion Assessment 
Stroke group
 
 • physical Assessment of upper-extremity sensorimotor functioning • NIH-SS 	Stroke Recovery Research Center or partly remotely [§]	3 – 3.5 hours

	
 • SIS[§] 		

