For the learning task-based data, a general linear model (GLM) will be fitted to each individual's data serving as the basis for the representational similarity analysis (RSA). In addition to the regressors of interest (matched to the onset time of each regressor of the event-related design of the learning-paradigm: 1st and 2nd order sequence force cues, random force cues) six motion parameters will be included as nuisance covariates. Estimated beta-values will be extracted from the GLM for each stimulus and run for each region of interest (ROI) within subject. For each ROI, a neural matrix will be created by correlating (Pearson) the multi-voxel patterns between all possible combinations of pairs of stimuli of the learning task condition and then averaged across subjects within group (first-order RSA⁵¹). In the second step, group-averaged matrices (only the upper diagonal elements) will be vectorized and correlated (Pearson) for all possible combinations of ROI pairs (second-order RSA⁵¹), which will allow to investigate the representational similarity between ROIs i.e., the clustering/networks of ROIs, with regard to the between-condition similarity in multi-voxel activation patterns.

For the resting-state data, the connectivity analysis will be used to identify physiological biomarkers for recovery and potential predictors for learning efficiency. For this purpose whole-brain resting-state network fluctuations, based on BOLD signal time courses, will be extracted for cortical and subcortical ROIs. Nuisance regression will be performed to account for the effects of motion on functional connectivity (including six translation and rotation parameters from the motion correction transformation, average CSF, white matter, and whole-brain time courses, as well as the first derivatives, squares, and squared derivatives of each of these confound predictors⁵². To extract the dynamic modulation of connectivity over time, time courses will be divided into sub-blocks of multiples of the TR to allow capturing slow-frequency fluctuations by approximating the frequency envelope of the hemodynamic response at the given TR with the highest possible temporal precision. Connectivity will be quantified as the magnitude-squared coherence^{53,54} between each pair of ROI for each sub-block of time⁵⁵. Network characteristics and their temporal dynamics will then be analyzed with dynamic network statistics following the approach given in reference⁵⁵.

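### The RSA plan does not restrict pattern pairs to different runs and gives no reference value for the region-to-region correlation, so regions with little pattern signal can look connected

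*Combined protocol and SAP*

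**What the plan says.** All of this stands in D3.2 (Analysis Plan), in the paragraph on the learning-task data.

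- Betas: "Estimated beta-values will be extracted from the GLM for each stimulus and run for each region of interest (ROI) within subject".
- First-order matrix, per region: "correlating (Pearson) the multi-voxel patterns between all possible combinations of pairs of stimuli of the learning task condition". These matrices are then averaged over participants within each group.
- Second-order step: "group-averaged matrices (only the upper diagonal elements) will be vectorized and correlated (Pearson) for all possible combinations of ROI pairs". The result is interpreted as the grouping of regions into networks.

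The section does not say how runs are combined. It mentions no cross-validation or noise whitening, and no null distribution, interval or threshold for the second-order r. The dynamic network statistics later in D3.2 concern the resting-state data only.

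On the task, D1.4 says that "a sequence of force levels is provided repetitively and contrasted with random force levels", and notes that conditions can be separated by side "as left and right hand will be tested". It does not say whether cues are blocked or intermixed, or whether participants share one order. D3.4 names building the RSA pipeline as a main purpose of the pilot, adds a conventional univariate connectivity analysis, and warns of limited power.

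**The concern.** Betas estimated from one run share that run's design matrix: overlapping haemodynamic responses and a common baseline make their errors covary. All regions of a participant are fitted with the same matrix, so the same error pattern enters every region's similarity matrix. The second-order step then correlates these matrices and cannot tell a shared error pattern from a shared representation.

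The caution in D3.4 is about power. This is bias, and a larger sample does not cure it. At stake is the Aim 1 network description: regions with weak pattern signal could be reported as connected, and the pipeline would carry that weakness into the follow-up proposal. Without a reference value, a reader cannot judge whether a given r is high or low.

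**Working it through.** The plan gives no figure for the RSA step, so there is none to reproduce. From the documents come TR 2 s and group sizes 25 and 15. Everything else below is assumed.

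**1. Mechanism.** With temporal noise covariance Ω, the beta errors of one run have covariance C = (X'X)⁻¹X'ΩX(X'X)⁻¹, times the voxel's noise variance. In a region without signal, the pattern correlation of stimuli i and j has expectation of about ρ_ij = C_ij/√(C_ii·C_jj). X is the same in every region, so ρ_ij is nearly the same in every region. For two patterns from different runs the expectation is 0, provided no noise with a stable voxel pattern carries over between runs.

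**2. Rough size.** Average same-run matrices over n participants and R runs, with V independent voxels. For small ρ_ij the sampling variance of an entry is about 1/(nR(V−1)). If τ² is the variance of the averaged ρ_ij over stimulus pairs, then second-order r ≈ τ²/(τ² + 1/(nR(V−1))).

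- One order for all participants, n = 15, R = 4, V = 20: 1/(15×4×19) = 0.00088. With τ = 0.03, r ≈ 0.0009/(0.0009 + 0.00088) = 0.51. With τ = 0.10, r ≈ 0.01/(0.01 + 0.00088) = 0.92. More participants raise r.
- A new order for each participant and run: τ² becomes τ₁²/(nR), where τ₁² is the single-run variance. Then nR cancels and r ≈ τ₁²/(τ₁² + 1/(V−1)). With τ₁ = 0.10, r ≈ 0.01/(0.01 + 0.0526) = 0.16. More participants neither help nor harm.
- Full stimulus-by-run matrix, 8 stimuli × 4 runs: 32 patterns, 496 pairs, of which 4×28 = 112 (0.226) are same-run. If same-run errors correlate δ on average and different-run errors 0, the shared variance is 0.226×0.774×δ² = 0.175δ², against 1/(15×19) = 0.0035. δ = 0.14 already gives r ≈ 0.0034/(0.0034 + 0.0035) = 0.49, whatever the cue order.

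**3. Pure-noise simulations, true r = 0.** Three separately written simulations, 4 runs each:

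- A: n = 15, 8 or 16 stimuli, spacing 2, 4 or 8 s, jitter 0 or 30%, 10 to 100 independent voxels; 108 settings, 36 replicates each.
- B: n = 25 and 15, 6 stimuli, 2, 4 or 12 s, 100 voxels, 20 replicates.
- C: n = 15, 8 stimuli, 2, 4 or 8 s, 20 voxels, 15 replicates.

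Mean spurious r:

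| Order and matrix | A | B | C |
|---|---|---|---|
| Blocked (B: one repeating order), same-run | 0.86 to 0.99 | 0.92 to 1.00 | 0.95 to 0.97 |
| Same, run-averaged betas | 0.57 to 0.98 | 0.76 to 1.00 | 0.83 to 0.89 |
| Intermixed, one order for all, same-run | 0.03 to 0.97 | 0.63 to 1.00 | 0.35 to 0.93 |
| Same, run-averaged | 0.03 to 0.90 | 0.31 to 0.99 | 0.13 to 0.79 |
| Intermixed, participant-specific, same-run | −0.03 to 0.72 | −0.10 to 0.78 | −0.03 to 0.33 |
| Same, run-averaged | −0.03 to 0.41 | −0.08 to 0.45 | about 0 |
| Full stimulus-by-run, all orders | 0.31 to 0.99 | 0.86 to 1.00 | 0.81 to 0.97 |
| Different-run pairs, all orders | −0.05 to 0.10 | −0.20 to 0.18 | −0.06 to 0.12 |

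In A at 8 s, participant-specific orders gave −0.03 to 0.14 (same-run) and −0.03 to 0.05 (run-averaged).

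**4. With unrelated true patterns (4 s spacing).** At signal SD 0.25, 0.5 and 1.0 of the noise SD, blocked same-run r was 0.85–0.92, 0.41–0.46 and 0.03–0.07; run-averaged it was 0.37–0.45, 0.06–0.07 and at most 0.02. Participant-specific orders gave at most 0.05 from 0.25 upward. Different-run pairs stayed within −0.03 to 0.03.

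**5. Why a reference is still needed.** In B, single different-run values of r had a 5th-to-95th percentile range of about −0.4 to 0.5 in typical settings. In A, noise region pairs rejected at a nominal 5% were:

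- label permutation on same-run matrices: 100% (blocked), 75–100% (one shared order), 5–47% (participant-specific);
- label permutation on different-run matrices: 4–8%;
- naive p-value on different-run matrices: 6–22%;
- null from noise passed through the design matrices: 3–10%.

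**6. Limit of different-run pairing.** Simulations A to C make noise independent between regions. A further run (8 intermixed stimuli, orders specific to participant and run, 4 s, n = 15, 4 runs) added one noise time course common to both regions, with voxel weights stable across runs. At 20/100 voxels, different-run r was 0.06/0.37 with 10% shared variance, 0.39/0.70 with 20% and 0.50/0.84 with 30%. A repeat at 20% gave 0.34 to 0.73. Label permutation on different-run matrices then rejected 39/94% at 20%.

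**The case against.** **This is missing detail, not a stated error.** It is true that the plan never says same-run pairs will be used. A reader might infer that it commits to a biased matrix; the text does not support that. What stands is that the text allows it, and that different-run pairing is a better rule for betas already extracted by run.

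**The size is assumed.** Also true. The same-run and run-averaged results run from about 0 to about 1. The highest come from blocked orders, which the documents neither state nor exclude; they call the design event-related, which fits blocked or intermixed cues. A reader might infer that the RSA networks will be artefacts. That does not follow: well-spaced, participant-specific orders or strong pattern signal leave little bias under same-run or run-averaged matrices.

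**Aim 1 rests on contrasts.** A reader might infer a spurious stroke-control difference or learning-stage change. Neither has been shown. In pure noise with the same type of design, A gave group differences of −0.03 to 0.06 and late-minus-early differences of −0.05 to 0.05. B had wider gaps, such as 0.45 (n = 25) against 0.31 (n = 15) for one shared order at 12 s, run-averaged. The formula in step 2 predicts this from unequal n: 0.31/0.69 × 25/15 = 0.749, so r ≈ 0.749/1.749 = 0.43. The spreads there are wide (0.04 to 0.84 and −0.35 to 0.68) and the inputs assumed, so it is no finding about this trial.

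**It is a pilot, with a univariate analysis alongside and no test claimed for r.** This limits the consequences. It does not validate the RSA networks.

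**Different-run pairing can itself be trusted too far.** This stands in full (step 6), and the noise null has to cover noise shared between regions.

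**Conclusion.** The concern holds as a minor to moderate point. D3.2 leaves same-run pairs in play and interprets the second-order r without a reference, so regions with little pattern signal can appear connected. The direction follows from the shared design matrix. The size depends on cue order, spacing, run handling, independent voxels and signal strength, which the documents seen here do not give; their absence is not counted against the plan. Under the assumed inputs, the pure-noise r is near 1 for blocked orders with same-run matrices. It is high for a full stimulus-by-run matrix in most settings, and about 0 for well-spaced, participant-specific orders under same-run or run-averaged matrices. Different-run pairs remove the design-driven part but not noise shared between regions.

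**What to change.** In D3.2:

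1. Where a hand and learning stage has at least two runs, compute the first-order matrix only from pattern pairs in different runs (cross-validated correlation or distance), using the betas already extracted per run.
2. Judge the second-order r against a null made by passing simulated noise through the actual design matrices, with noise matched to the GLM residuals in time, across voxels and jointly across regions. Do not rely on label permutation or a naive p-value alone.
3. Where only one run exists, keep the planned matrix, label it exploratory, and report it only against that null.

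The cost is SAP wording and analysis code; no added scanning is required. There are two downsides.

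- Estimates are somewhat noisier. With identical true patterns in two regions at signal SD 0.25 of the noise SD, different-run r was 0.71–0.95 against 0.83–0.97 for run-averaged betas; at 0.5 it was 0.94–0.99.
- The null is only as good as its noise model. Assuming half the true number of independent voxels, the same-run null rejected 61–100% of noise pairs in blocked designs and 4–49% in intermixed ones. With residual-matched noise it rejected 4–10%. That check did not include noise shared between regions, so the joint matching in item 2 should be tested before use.

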We still do not know enough about how a focal lesion impacts the dynamics within brain circuits that govern motor learning and how this relates to maladaptive plastic changes. Filling this knowledge gap builds the basis for designing interventions that causally target experience-dependent maladaptive changes which negatively impact the patient's recovery (e.g., leading to disuse of the paretic hand). With this JI project, we will generate pilot data serving as the first evidence for motor learning-related network dynamics in the chronic phase after stroke (aim 1) and their link with biomarkers of recovery of upper-extremity sensorimotor function (aim 2).

AIM 1 To characterize motor learning (ML)-related neural network dynamics in the presence of a focal lesion, we will use a representational statistical modeling approach¹⁸ to describe learning-related connectivity changes based on task-based functional magnetic resonance imaging (fMRI) in stroke survivors (≥ 6 months post-lesion, stroke group SG) and healthy volunteers of comparable age and gender (control group, CG). Functional connectivity patterns will be modeled throughout the acquisition phase to capture the temporal trajectory of encoding-related network changes.

AIM 2 To understand the association between ML-related network dynamics and biomarkers of recovery, we will comprehensively describe upper-extremity sensorimotor functioning and impairment for the individuals in the SG and statistically integrate these biomarkers of recovery with the ML-related network dynamics within a separate representational model.

B. BACKGROUND AND SIGNIFICANCE

Recovery of upper extremity function remains dissatisfying for the majority of stroke survivors with sensorimotor impairment¹⁹, which represents a major hindrance to independence in daily life²⁰. Within the field of rehabilitation research, learning mechanisms have long been a major area of interest because they are considered one key player in functional recovery. This basic premise goes back to seminal work that established the brain's capacity to change in response to environmental stimuli and learning, i.e., experience-dependent plasticity^{21,22}.

However, it is evident that plasticity does not have purely beneficial effects on recovery³ but that also negative consequences such as learned disuse of the paretic hand can be observed¹.

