Physical Assessment of upper-extremity sensorimotor functioning. To comprehensively characterize a broad range of upper extremity sensorimotor control, a test battery will be used that captures the non-/low-functional up to fine-motor impairment level. Passive and active range of motion and movement-associated pain of the paretic upper extremity will be evaluated with the upper-extremity section of the Fugl-Meyer Assessment (UEFMA)³¹. To characterize grasp, grip, pinch, and gross-motor functioning with relevance to activities of daily living, the Action Research Arm Test will be used (ARAT)^{32,33}. To quantify dexterity of individual finger movements, the Nine-Hole Peg Test (9HPT)^{34,35} will be used. To quantify maximum voluntary contraction (MVC) and repeated contraction/release of contraction, a digital dynamometer will be used. All physical examination will be performed by a study therapist trained in standardized testing of upper-extremity function.

Neuro-Cognitive and emotion Assessment. To further ensure eligibility, an in-person session will take place. Following consent, the Montreal Cognitive Assessment (MoCA)³⁶ will be completed. Participants will complete computerized cognitive tests from the NIH Toolbox³⁹ (30-40 minutes). Each of these tests has been extensively normed compared to traditional neuropsychological measures. Tests from different batteries will be utilized in this study to optimize a comprehensive but efficient, reliable, and minimally burdensome subset of tests for chronic stroke patients. Participants of the SG presenting with aphasic symptoms will also complete the bedside Western Aphasia Battery (WAB)³⁷, to measure levels of aphasia that would preclude valid assessment in all other domains. Similarly, participants will complete the Virtual Reality Lateralized Attention Test (VRLAT)³⁸ if suspected of presenting with neglect symptoms.

The Patient Health Questionnaire-9 Item (PHQ-9)⁴¹ will be administered to screen for depression and anxiety as these are relevant confounders for learning and memory.

All neuro-cognitive and emotion assessment will be performed by trained personnel and overseen by a licensed clinical psychologist ([name]).

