3	
MRI scanning and task familiarization
 
 • MRI Safety Screen • Sleep and vigilance screening 
MRI sequences:
 
 • FLAIR • DWI • ASL • T2* weighted sequence (resting-state) • Physiological recordings 
Learning task:
 
 • Task familiarization (in the mock scanner) 	Center for Biomedical Imaging	2 – 2.5 hours
4	
MRI scanning during task practice
 
MRI Safety Screen
 
Sleep and vigilance screening
 
MRI sequences:
 
 • High-resolution T1 weighted • T2* weighted sequence (task-based) during task practice • Physiological recordings 	Center for Biomedical Imaging	2 – 2.5 hours

D3. DATA ANALYSIS

D3.1 Sample Size Justification.

Given the scarcity of pilot data on stroke and control participants and fMRI-based dynamic connectivity during motor learning, justification has to be based on our best estimates and regarded with some caution. One of the primary goals of this project is to determine effect sizes for the follow-up grant proposal. For changes to latent connectivity characteristics induced by implicit motor learning (pre/post evaluation), empirically obtained effect size estimates were derived from the average effect size of published studies involving participants with chronic stroke⁹ and healthy volunteers⁵⁰. Consequently, sample sizes of 25 and 15 in the stroke survivors and healthy volunteers will allow us to estimate the for the main effect of time (pre/post learning) the within-group effect sizes can be expected to be in the range of 0.33 - 0.52 at 90% confidence level.

D3.2 Analysis Plan.

Imaging Preprocessing. Data will be processed by the CBI Computational Core led by [name]. Preprocessing parameters for the task-based fMRI data will be optimized to fit the requirements of the representational similarity analysis (RSA, described below), specifically smoothing will be reduced to allow for better multivariate pattern detection. Resting-state fMRI data will undergo in-house standard preprocessing.

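### The task-fMRI RSA averages matrices within group before correlating ROIs, so this step alone gives no participant-level network value or interval, and its correlations are not comparable between groups of 25 and 15

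*Combined protocol and SAP*

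**What the plan says.** D3.2 sets out the task-based RSA in this order:

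1. A GLM is fitted per participant. "Estimated beta-values will be extracted from the GLM for each stimulus and run for each region of interest (ROI) within subject".
2. Stimulus-by-stimulus correlation matrices are formed per ROI; these are "then averaged across subjects within group". The plan calls this first-order RSA.
3. The between-ROI stage comes last: "group-averaged matrices (only the upper diagonal elements) will be vectorized and correlated (Pearson) for all possible combinations of ROI pairs".

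The stated use of the third step is to show "the clustering/networks of ROIs, with regard to the between-condition similarity in multi-voxel activation patterns". D3.2 names no interval, resampling scheme or group test for it, and does not say how runs enter the matrices.

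Elsewhere the plan asks for results at participant level:

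- D3.1 sets this goal: "One of the primary goals of this project is to determine effect sizes for the follow-up grant proposal". Its planning range, with confidence set at 90%, is worded thus: "main effect of time (pre/post learning) the within-group effect sizes can be expected to be in the range of 0.33 - 0.52". The groups are 25 stroke survivors and 15 healthy volunteers.
- Aim 2 sets out to characterise "upper-extremity sensorimotor functioning and impairment for the individuals in the SG and statistically integrate these biomarkers of recovery with the ML-related network dynamics". This is to be done in its own representational model.
- D3.4: setting up the RSA pipeline is a main purpose of the pilot, and a conventional univariate connectivity analysis is also included. Its method is not given.

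**The concern.** A standardized change needs a mean and a between-participant SD. An association with recovery measures needs one network value per stroke participant. Once matrices are averaged within group, the relation between two ROIs is a single number per group and neither quantity can be recovered from it. If the pipeline is run as written, and nothing else is specified for the task data, the pilot would end with descriptive matrices and no effect size from its main method to carry into the follow-up application.

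A second consequence bears on Aim 1. A correlation between two averaged matrices is pulled towards zero by the noise left after averaging, and that noise shrinks as more participants are averaged. With 25 against 15, the stroke group's correlations would tend to be higher even if nothing differed between the groups.

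**Working it through.** **The plan's own figure.** D3.1 gives 0.33 to 0.52 at 90% confidence. Read as a 90% half-width for a standardized within-group mean, 1.645/√25 = 0.329 matches the lower end, but 1.645/√15 = 0.425 does not match the upper. The inputs (published effect sizes, pre/post correlation) are not given, so the range can be neither confirmed nor refuted. The present point does not depend on it.

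**Counting values.** With R ROIs (number not given) there are R(R−1)/2 pairs. Take R = 10 as an assumption, so 45 pairs.
- As written: 2 × 45 = 90 correlations, one per pair per group, with 0 degrees of freedom for a between-participant SD.
- Correlated within participant: 40 × 45 = 1,800 values, that is 25 and 15 per pair, with 24 and 14 degrees of freedom.

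**Effect of unequal group size.** Assume that each ROI matrix has a true pattern with variance c² across cells, that each participant adds independent noise of variance 1, and that the true between-ROI correlation is ρ = 0.60 in both groups. The correlation of the averages over n participants is approximately ρ × c²/(c² + 1/n). With c = 0.3 (c² = 0.09):
- n = 25: 0.60 × 0.09/(0.09 + 0.0400) = 0.415
- n = 15: 0.60 × 0.09/(0.09 + 0.0667) = 0.345
- within one participant: 0.60 × 0.09/1.09 = 0.050, whatever the group size

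Simulation with 66 cells (12 stimuli, assumed) gives 0.41, 0.34 and 0.05. The gap depends on c², which the documents do not give:

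| c² (assumed) | n = 25 | n = 15 | gap |
|---|---|---|---|
| 0.05 | 0.33 | 0.26 | 0.08 |
| 0.09 | 0.42 | 0.34 | 0.07 |
| 0.20 | 0.50 | 0.45 | 0.05 |
| 0.50 | 0.56 | 0.53 | 0.03 |

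The direction is the same throughout; the size is not known.

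**Cost of the participant-level route.**
- *Attenuation.* Suppose the true r rises from 0 to 0.60 with learning (a large change, assumed), with independent noise and P stimulus pairs. Then d ≈ atanh(0.60 × reliability)/√(2/(P−3)). To reach d = 0.33 to 0.52, reliability must be about 0.16 to 0.24 with P = 28, or 0.07 to 0.11 with P = 120.
- *Shared noise.* If two ROIs share noise within a run, the participant-level r is inflated. With no true correlation, noise correlation 0.10 and c² = 0.09, it is 0.10/1.09 = 0.09.

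**What the sample allows.** The 90% half-width of a standardized change is t(0.95, n−1)/√n: 1.711/√25 = 0.34 and 1.761/√15 = 0.45. These widths come from the sample size, not from the order of operations, and are not evidence of harm.

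**The case against.** The strongest reply is that the plan gives the second-order step a descriptive purpose, for which group averaging is a sound choice in a noisy pilot: under the assumptions above it yields 0.34 to 0.41, against 0.05 within a participant. D3.1 speaks of connectivity change, not representational similarity. Aim 2 has its own model. The covariates in D3.3 belong to follow-up analyses that are not tied to RSA. D3.4 concedes that RSA benefits from large samples and adds a univariate analysis.

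Much of this stands. A reader might infer that the pilot cannot estimate effect sizes or address Aim 2 at all. The documents do not support that: they nowhere make second-order RSA the sole source of those results, and the resting-state coherence analysis could yield participant-level values, although not of the network during task learning. A reader might also infer that between-participant variation is lost for good. It is not: participant matrices exist before averaging, and resampling participants would give an interval for the group result.

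What remains is that the only task-network analysis whose steps D3.2 spells out stops at group level, and that the univariate analysis and the Aim 2 model are named without a method. The reply does not touch the unequal-size problem, which affects even a descriptive side-by-side reading of the two groups. The warning about shared within-run noise is sound and shapes the fix.

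**Conclusion.** The point holds in a limited form and should be fixed before analysis. That the group-averaged RSA gives no participant-level value and no interval follows from the written order of steps and rests on no assumption. That it cannot by itself serve the effect-size goal or Aim 2 follows directly.

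The lack of comparability between groups of 25 and 15 is certain in direction when true similarity and noise are equal in both groups. Its size, about 0.41 against 0.34 in the main illustration, rests on assumed noise, an assumed true r of 0.60 and independence between participants. The data to be collected are not at fault; only the specified analysis needs to change.

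**What to change.** In D3.2:

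1. **Keep the group-averaged matrices as description**, and give intervals by resampling participants and re-averaging. Use a jackknife or a bias-corrected bootstrap: drawing with replacement adds noise to the average, so a plain percentile interval would sit too low.
2. **Make any stroke-control comparison of group matrices fair to group size**, either with equal numbers (for example repeated subsamples of 15 stroke participants) or by permuting subject labels and re-averaging at 25 and 15. Equal numbers do not equalise noise per participant, which is one reason for item 4.
3. **Add a second-order correlation within each participant**, per ROI pair and learning phase, Fisher z-transformed. Where the number of runs allows, correlate one ROI's matrix from one run with the other ROI's matrix from a different run, so that shared within-run noise does not inflate the value. Use these values for the within-group change with a 90% CI and for Aim 2.
4. **Report the reliability of the participant-level values by group.**
5. **State which measure supplies the effect sizes and Aim 2**, and describe the univariate analysis and the Aim 2 model if either is meant to do so.

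The cost is wording and scripting; per-participant, per-run betas are already planned. The drawback is noise and attenuation. At low reliability even a large true change would give a small d, and the documents give neither the reliability nor the number of stimulus pairs and runs. With few runs per phase, cross-run correlation may not be possible, and the shared-noise caveat would then have to accompany the result.
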